## 3.2 Laboratory Endpoints:

The first approximately 62 patients who are enrolled will be analyzed as a sub-study of continuous lab outcomes comparing those on metformin versus placebo: C-reactive protein (CRP) level; albumin level; viral load; as well as microbiome changes (stool sample is optional for participants), from baseline to days 5 and 10. (See Section 13 for more information)

\*Patients will be asked to take a second reading if they have a reading  $\leq 93\%$  and to hold a handwarmer for 5 minutes first to obtain good blood flow; to take the reading while sitting up; and advised to place the oximeter on the 4th finger (where skin is thinner).

## 4.0 Investigational Products

#### 4.1 Description:

Metformin: a biguanide, administered in its immediate release (IR) formation, 1,500mg by mouth (typical dose for clinical use is 2,000mg per day). Patients will be instructed to take 500mg once on Day 1, ideally in the PM; 500mg in the AM and PM of Days 2-5; and 500mg in the AM and 1,000mg in the PM of Days 6-14.

*Fluvoxamine*: an antidepressant, administered in twice daily dosing, 50mg twice per day for 14 days (typical dose for clinical use is 100mg to 300mg per day).

*Ivermectin*: is an antiparasitic medication administered typically in ranges of 200-800mcg/kg/day. In order to stay within this dose range, the following doses will be given in the following weight categories: 74 kg - 88 kg = 35 mg; 88kg - 106kg = 42mg; 106-124kg = 49mg; >124kg = 56mg. See details in Section 4.2. Treatment will be given for 3 days, and the remaining 11 days will be placebo tablets that exactly match the ivermectin in order to protect the blind.

4.2 Rational for formulation and dose:

Metformin: Given the current recall of Metformin Extended Release, ER, (see section on FDA recall below), availability of ER is limited. Additionally, it is possible that additional lots of ER will be recalled, further complicating supply issues and exposure to the recalled substance to patients. The side effect profile of immediate and extended release is similar, and we are limiting the dose at 1,500mg daily to balance the need to achieve a consistent dose and an effective dose without causing side effects, as the risk of side effects increase at a dose of 2,000mg daily.

*Fluvoxamine*: A dose of 100mg TID was recently used in a small randomized trial, and 50mg BID were recently used in a prospective cohort study. The higher dose elicited side effects in approximately 10% of participants. A separate ongoing phase III trial is now testing 100mg BID. We feel it is important to test a lower 50mg BID dose as the risks of side effects is lower and the public may be more willing to take an antidepressant medication if it is low dose. Additionally, the risk of serotonin syndrome and other drug interactions that may occur with fluvoxamine is lower with a lower dose, and thus persons currently on a serotonin reuptake inhibitor (SSRI) would not have to stop or alter their current therapy.

*Ivermectin:* we are using the standard release formulation (and only formulation) of ivermectin tablets. Given our lower BMI limit of 25kg/m^2, we do not anticipate enrolling many individuals weighing < 74kg. If someone weighs < 74kg or >124kg enrolls, the RC will contact the lead pharmacy for guidance on individual dispensing (regardless of treatment allocation, as the RC will be blinded to this), to keep the dose within approximately 390-470mcg/kg/day for the majority of patients, 350mcg/kg/day-480mcg/kg/day for all patients.

- We anticipate that most individuals enrolled will weigh between 68-104kg.
  - 35mg/day: is 390-470 mcg/kg/day for body masses of 74 to <88kg

- 42mg/day: is 390-470 mcg/kg/day for body masses of 88 to <106kg.
- 49mg/day: is 390-470 mcg/kg/day for body masses of 106 to <124kg
- 56mg/day: is 390-470mcg/kg/day for body masses of >=124kg

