## 6.0 Study Population

6.1 Study Population:

Adults age 30-85 years with no prior history of SARS-CoV-2 infection and with BMI in overweight or obesity category. We will not exclude patients who have diabetes, but we will exclude patients on insulin or a sulfonylurea. Symptoms are not a requirement to enroll in the because of their subjective nature and because of wanting to start patients on study drug early in the disease course.

6.2 Inclusion and Exclusion Criteria:

Inclusion criteria	Exclusion criteria
- Positive laboratory test for active SARS-CoV-2	- Hospitalized, for COVID-19 or other reasons.
viral infection based on local laboratory standard	- Symptom onset greater than 7 days before
(i.e. +PCR) within 3 days of randomization.	randomization (symptoms not required for inclusion).
- no known history of confirmed SARS-CoV-2	- immune compromised state (solid organ transplant,
infection	bone marrow transplant, AIDS, on chronic high dose
- Age $\geq$ 30 years and $<$ 85 years	steroids)
- BMI $\geq 25$ kg/m  by self-report height/weight or	- Hepatic impairment (Child-Pugh B and C) or
$>= 23 \text{kg/m}^2$ in patients who self-identify in	that in the opinion of the investigator, would affect safety
Asian or Latinx background. 	- Inability to obtain informed consent
- Has an address and electronic device for	- Enrollment in another blinded RCT for COVID-19
communication	- Already received an effective (FDA approved/EUA*)
- GFR>45ml/min within 2 weeks for patients	therapy for COVID-19 (currently monoclonal antibody
>75 years old, or with history of heart, kidney, or	treatment)
liver failure.	- Alcohol use disorder

- Other unstable medical condition or combination of home medications that in the view of the PI make it unsafe for the individual to participate

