- We are requiring a baseline GFR in persons > age 75, or with history of heart, liver, or renal failure, within 2 weeks before enrolling to ensure those high risk patients have a GFR > 45.

Fluvoxamine:

- We are using a low dose of fluvoxamine with only 1 dose on the first day to mitigate side effects from BID dosing on the first day.
- Ivermectin:
- While the range of acceptable and safe per kilo doses of ivermectin is large, we are using weight-based dosing.

All arms:

- We will use careful screening of exclusion criteria so that participants are excluded from arms that may include a contraindication or medication interaction.
- We are recommending that study drug be taken at the end of a small meal, and that patients abstain from alcohol use during the study period.
- We are creating an upper age limit in order to reduce the likelihood of a patient experiencing reduced GFR during the study period.
- Patients will be advised to let their providers know that they are in a research study that involves metformin, ivermectin, or fluvoxamine, and thus that they should discontinue the study medication at the time of hospitalization or before a CT scan with contrast.
- Every effort will be made to enter a Research Note into the electronic health record stating that the patient is in a double-blinded randomized trial of metformin, fluvoxamine, ivermectin, and placebo with the study number and contact information for participants who are enrolled from participating health systems.
- 9.2 Reproduction Risks:

While fluvoxamine and ivermectin may be used in pregnancy and have no known teratogenic effects, they have not been assessed in prospective randomized trials in pregnancy as often as metformin has. Thus, we will close the randomization arms that include ivermectin or fluvoxamine to pregnant women. We will have a separate group of blinded study packs for pregnant and lactating women, so that study staff will know that pregnant and breastfeeding participants are getting only either metformin or placebo, but will remain blinded to whether they are receiving metformin or placebo. Additionally, because pregnant and lactating women will be considered their own sub-study in this trial, and an important sub-study, we will enroll pregnant/lactating women down to age 18 years old. Thus, pregnant women may be analyzed as a separate substudy.

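### Ivermectin 56 mg/day meets the stated 390-470 mcg/kg/day only up to about 143 kg, not at every weight from 124 kg; and the Section 9.1 meal advice omits ivermectin's empty-stomach exception (both minor)

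*Protocol*

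**What the plan says.** **Dose.** Section 4.1 describes ivermectin with the words "is an antiparasitic medication administered typically in ranges of 200-800mcg/kg/day" and then assigns fixed doses by weight, ending with "106-124kg = 49mg; >124kg = 56mg". It points to Section 4.2 for details. Section 4.2 lists the same four doses and gives 390-470 mcg/kg/day for each. The first three weight bands have an upper limit. The last does not: "56mg/day: is 390-470mcg/kg/day for body masses of >=124kg".

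The paragraph before that list contains a safeguard: "If someone weighs < 74kg or >124kg enrolls, the RC will contact the lead pharmacy for guidance on individual dispensing". Its purpose is to keep the dose within roughly 390-470 mcg/kg/day for most participants and within "350mcg/kg/day-480mcg/kg/day for all patients". Section 4.2 adds: "We anticipate that most individuals enrolled will weigh between 68-104kg". Section 6.1 describes adults "with BMI in overweight or obesity category", and the criteria in Section 6.2 set a minimum BMI but no maximum BMI or weight.

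**Food.** Section 4.5 tells participants to take ivermectin and its matching placebo without food, and limits the with-food advice to metformin, fluvoxamine and their placebos. The medication regimen repeats the empty-stomach rule for blister-packed tablets. Section 9.1, in its list for all arms, says: "We are recommending that study drug be taken at the end of a small meal". It makes no exception.

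**The concern.** A fixed dose over an open-ended weight band cannot stay inside a mcg/kg range, because the dose per kilogram keeps falling as weight rises. The last line of Section 4.2 therefore has to fail at some weight, and the trial recruits from a population in which high weights occur. At stake is under-dosing of the heaviest participants relative to the protocol's own target if staff or pharmacy take 56 mg as the settled answer. The protocol gives those participants both a fixed dose and an individually set dose.

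The food point is a direct conflict between a general sentence and two specific ones. Section 9.0 gives the end-of-meal reasoning for metformin only. Section 4.4 notes that a high-fat meal may raise ivermectin absorption, so the protocol itself treats food as relevant to this drug. It gives no figure, and no size of food effect is claimed here.

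**Working it through.** **Inputs.** Doses and weight bands are from Sections 4.1 and 4.2. The target (390-470) and the bound for all patients (350-480) are from Section 4.2. The wider typical range (200-800) is from Section 4.1. All ranges are in mcg/kg/day.

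**Formula.** mcg/kg = dose in mg × 1000 / weight in kg. In reverse, weight = dose in mg × 1000 / (mcg/kg).

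**Step 1: reproduce the three closed bands.**

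| Dose | At lower edge | At upper edge |
|---|---|---|
| 35 mg, 74 to 88 kg | 35000/74 = 473.0 | 35000/88 = 397.7 |
| 42 mg, 88 to 106 kg | 42000/88 = 477.3 | 42000/106 = 396.2 |
| 49 mg, 106 to 124 kg | 49000/106 = 462.3 | 49000/124 = 395.2 |

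These match 390-470 apart from an excess of 3 to 7 at the lower edges of the first two bands. All stay inside 350-480 over their whole width, so this is the protocol's own calculation.

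**Step 2: the open band, 56 mg.**

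| Weight (kg) | mcg/kg |
|---|---|
| 124 | 451.6 |
| 143 | 391.6 |
| 143.6 | 390.0 |
| 150 | 373.3 |
| 160 | 350.0 |
| 170 | 329.4 |
| 280 | 200.0 |

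In reverse: 56000/390 = 143.6 kg is where the target is lost, 56000/350 = 160 kg is where the floor for all patients is lost, and 56000/200 = 280 kg is where the typical range is lost. At 170 kg, 329.4/350 = 0.941, about 6% under the floor.

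**Step 3: who is affected.** The protocol gives no share of participants above 143 kg. Taking heights of 1.65 to 1.85 m as an assumption, BMI = weight / height²:

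- 143.6 kg: 143.6/1.65² = 52.7, down to 143.6/1.85² = 42.0.
- 160 kg: 160/1.65² = 58.8, down to 160/1.85² = 46.7.

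The group is probably small, but nothing in the criteria excludes it.

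**Step 4: the food instructions.** Section 4.5 and the medication regimen agree: ivermectin and its placebo without food, the other tablets with food. Section 9.1 gives one rule, after a small meal, for study drug in all arms. Two of the six arms contain ivermectin. Read literally, Section 9.1 cannot be followed together with the other two. The advice on mild side effects in Section 4.5 also mentions meals, but it follows the split by drug and reads naturally as applying to tablets already taken with food. It is not counted as a conflict.

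**The case against.** On the dose, the strongest reply is that the case is already handled in the same paragraph. Everyone above 124 kg goes to the lead pharmacy, with 350-480 mcg/kg/day as the bound, so a protocol-compliant participant above 160 kg never receives a flat 56 mg. Section 4.1 sends the reader to Section 4.2, and its own 200-800 range is met up to 280 kg. This stands as a limit on the consequences. It does not make the line true, and it leaves two places that fix 56 mg for the people who are meant to be dosed individually. Below 74 kg, by contrast, neither list fixes a dose.

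It can also be said that the first two bands exceed 470 at their lower edges and are excused by the word approximately, which is in the paragraph but not in the list. That is fair for a strictly literal reading. The difference is that their excess is bounded at about 7 and stays within 480, whereas the shortfall in the open band grows with weight and passes the floor.

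On food, Section 9.1 is a summary of risk mitigation and the operative directions elsewhere are clear. In the full factorial every participant also takes metformin or its placebo, so the meal advice suits at least one tablet in each arm. That softens the conflict, but the sentence still lacks an exemption.

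**Conclusion.** Both points hold, and both are minor. The dose statement for 124 kg and above is correct from 124 to about 143 kg and false beyond that; a flat 56 mg would miss the protocol's own floor above 160 kg. The error is toward under-dosing only, and the pharmacy referral prevents it when followed. No fault is claimed for doses from 74 to 124 kg. That few people are affected rests on the expected 68-104 kg weights and the assumed heights, since the protocol gives no distribution. The Section 9.1 sentence is one unqualified general statement set against two specific and consistent instructions. Neither point affects the endpoint, sample size, error rates or analysis.

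**What to change.** 1. In Section 4.1 and the last dose line of Section 4.2, limit 56 mg to 124 to about 143 kg. State that above this weight the lead pharmacy sets the dose within 350-480 mcg/kg/day. One further 7 mg step shows that the range is attainable: 63 mg gives 63000/144 = 437.5 at 144 kg and 63000/180 = 350.0 at 180 kg.
2. The existing referral of everyone above 124 kg can stay. To avoid two rules for 124 to 143 kg, say that 56 mg is the pharmacy's default there.
3. In Section 9.1, exempt the blister-packed tablets (ivermectin and its matching placebo) from the meal advice.
4. Optionally, say in Section 4.5 that the mild-side-effect advice on meals covers metformin, fluvoxamine and their placebos.

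The cost is a few words in each place. Blinding is unaffected, because the exemption covers the blister-packed tablets whether active or placebo.

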#### Acquisition:

A sufficient quantity of the FDA-approved formulation of metformin IR, ivermectin, and fluvoxamine IR for the study has been acquired by the MHealth Fairview IDS pharmacy.

4.3 Storage and Stability:

Store at room temperature up to 30°C. Dispense in a tight, light-resistant container.

4.4 Pharmacokinetics:

*Metformin:* Intravenous single-dose studies in normal subjects demonstrate that metformin is excreted unchanged in the urine and does not undergo hepatic metabolism (no metabolites have been identified in humans) nor biliary excretion. Renal clearance is approximately 3.5 times greater than creatinine clearance, which indicates that tubular secretion is the major route of metformin elimination. Following oral administration, approximately 90% of the absorbed drug is eliminated via the renal route within the first 24 hours, with a plasma elimination half-life of approximately 6.2 hours. In blood, the elimination half-life is approximately 17.6 hours, suggesting that the erythrocyte mass may be a compartment of distribution.

*Fluvoxamine:* Onset of action: Anxiety disorders (obsessive-compulsive, panic, and posttraumatic stress disorder): Initial effects may be observed within 2 weeks of treatment, with continued improvements through 4 to 6 weeks (Issari 2016; Varigonda 2016; WFSBP [Bandelow 2012]); some experts suggest up to 12 weeks of treatment may be necessary for response, particularly in patients with obsessive-compulsive disorder and posttraumatic stress disorder (BAP [Baldwin 2014]; Katzman 2014; WFSBP [Bandelow 2012]). Depression: Initial effects may be observed within 1-2 weeks of treatment, with continued improvements through 4- 6 weeks (Papakostas 2006; Posternak 2005; Szegedi 2009; Taylor 2006). Distribution: Vd: ~25 L/kg

Protein binding: ~80%, primarily to albumin

Metabolism: Extensively hepatic via oxidative demethylation and deamination

Bioavailability: Immediate release: 53%; Extended release: 84%; not affected by food.

Half-life elimination: ~14 to 16 hours; ~17 to 26 hours in the elderly

Time to peak, plasma: 3 to 8 hours

Excretion: Urine (~85% as metabolites; ~2% as unchanged drug)

*Ivermectin:* Absorption: Well absorbed in the fasting state (Baraka 1996; Edwards 1988; Okonkwo 1993); may be increased with a high-fat meal (Duthaler 2020; Guzzo 2002; Miyajima 2013). Distribution:  $V_d$ : 3.1 to 3.5 L/kg in healthy volunteers; mean 9.9 L/kg (range: 6.9 to 15.3 L/kg) in patients with onchocerciasis; high concentration in the liver and adipose tissue; does not readily cross the blood-brain barrier (Gonzalez Canga 2008; Okonkwo 1993). Protein binding: ~93% primarily to albumin (Gonzalez Canga 2008) Metabolism: Hepatic via CYP3A4 (major), CYP2D6 (minor), and CYP2E1 (minor) Half-life elimination: 18 hours Time to peak, serum: ~4 hours Excretion: Feces; urine (<1%)

#### 4.5 Dose Modification:

Participants will be advised to take ivermectin and its matching placebo on an empty stomach with water. Ivermectin and its matching placebo are provided in asmall blister-packed square.

Participants will be advised to take all other medications (i.e., metformin and/or fluvoxamine and their matching placebos) with a small amount of food (not on an empty stomach).

With mild side effects, participants will be reminded to take the tablets at the end of a meal, as opposed to the beginning of or "with" a meal. They will also be advised to stay upright for about an hour after consuming the study tablet.

With mild-moderate side effects, if the patients find them tolerable, patients will be advised the above, and that side effects should decrease after about 5 days of the medication. With moderate or moderate-substantial side effects that the patient finds intolerable, participants will be advised that they can break tablets in half if they feel they are having a non-tolerable medication side effect. Each type of active drug and placebo pill in this study can be broken in half. Dose modification will be recorded in the study database.

In the event of substantial side effects, participants may discontinue the study medication and stay in the study to complete follow up. This treatment discontinuation (whether in the placebo or any active treatment group), will not be considered study withdrawal.

4.6 Placebo:

The placebo will be tablet of microcrystalline cellulose, made to exactly mimic metformin or fluvoxamine or ivermectin.

4.7 Study Drug Handling:

Fairview IDS, part of M Health Fairview, will oversee the study and provision of bulk and prepackaged study drug (including placebo) to participating sites. Participants will be given a study number coded by site (e.g. 01-001, 02-001, etc.). The pharmacy team involved will be unblinded to patient randomization. All other members of the clinical care team and the participants will be blinded to treatment allocation. The research team statisticians will remain blinded (additional information in Section 13, Statistical Considerations).

The IDS pharmacy will oversee the pre-packaging of the study drug into 2-week AM/PM pill packs for patients to improve compliance with the study drug regimen, improve safety (so they take the right number of each type of medication pill), and facilitate delivery to patients on the day of their consent. The research staff or pharmacy will select study drug based on the randomization code that preserves blinding, place the patient's name and study ID in the drug accountability log and study database, and place it in the study box for that patient and arrange for the delivery.

Pill packs will be labeled with the study name and PI name, contact information about the study; and the names and doses of all potential study drugs.

4.7.1 Provision of study drug to patients:

Following randomization, study drug to participants in an expedited way (for example courier, overnight mail service).

4.8 Study Unblinding:

Each participating pharmacy team, or the central pharmacy, will hold the blind for their site. Each site will have 24-hour access to the blind. Each subject will be provided information as to whom to contact for unblinding information in the event of an emergency. There is one unblinded statistician with two unblinded supporting statisticians on the study team.

- 4.8.1 Multiple strategies will be developed to assure that study drug is stopped at the time of hospitalization (as metformin is typically stopped at hospitalization for safety reasons)
- 4.8.2 Multiple strategies will be developed to inform patients and their medical providers that they are in study involving metformin or fluvoxamine or ivermectin, and that it should be stopped prior to imaging studies with contrast.
- 4.8.3 Multiple strategies will be developed to inform patients' medical providers that they are in a study involving metformin or fluvoxamine or ivermectin, and thus any potential interacting medications, or metformin itself, should not be started while the patient is in the study. The patient may withdraw consent at any time.
- 4.9 Biosafety:

Patient samples will be carried in an expedited way (i.e. courier or mail services) in packaging that is approved for Biologic Substances Category B, UN 3373, per CDC guidelines for shipping SARS-CoV-2 samples: https://www.cdc.gov/coronavirus/2019-ncov/lab/lab-biosafety-guidelines.html#specimen

[figure not shown]
## 5.0 Study Procedures

5.1 Study Design:

Double-blinded, factorial, placebo-controlled randomized trial comparing metformin vs fluvoxamine vs ivermectin vs metformin + fluvoxamine vs metformin + ivermectin vs placebo for outpatient treatment of COVID-19 disease. This is an outpatient study. Study drug will be stopped at the time of hospitalization for any reason.

Overview of Study\*:

### VERSION 3.4

\*Updated sample size: 225 per arm, 1,350 total.

5.2 Recruitment

Advertising may be done by approaching patients who are scheduled to come for PCR testing, prior to or after their SARS-CoV-2 screening test, and before or after they may have the results. Advertising to patients before their SARS-CoV-2 test result is back allows the patients to consider the study and read about metformin and discuss with family. Receiving a positive SARS-CoV-2 test result will be overwhelming and make it challenging for patients to fully consider whether or not they want to participate. Being informed of the study before results are known will facilitate enrolling soon after their result is known so that study medication can be started early in the course of disease or soon after exposure.

Clinical teams may refer patients to the study in person or over the phone, including transferring patients to the study phone line if they are willing to be transferred. RC's may reach out to close contacts of persons with positive SARS-CoV-2 infection, and/or respond to patient emails, phone calls, or inquiries on the study website. The study teams may receive lists of persons who reach out to community patient advocacy groups looking for trials to enroll into. The central and participating site study teams may receive names and phone numbers of persons with a positive SARS-CoV-2 result from other facilities conducting testing. This information will only be in a secure database (Redcap or Box).

Patients may be given a brochure or electronic message with study information for contacting the study team if interested in this clinical trial. RC's may also pro-actively reach out to patients who are scheduled for SARS-CoV-2 testing or recently underwent SARS-CoV-2 testing either before or after they receive test results, as not all patients may receive or read an electronic message or brochure.

Patients can also self-refer based on seeing advertisements (such as through all forms of social media, newspaper, local posters, and email referrals).

Patients receiving test results by phone from the clinical care team may be alerted they may qualify for a research study and that study team members may contact the patient about eligibility.

Every attempt will be made to make sure the clinical team is informing patients of their SARS-CoV-2 testing results rather than the research team.

At times recruitment and enrollment efforts may be focused on priority populations within the eligibility criteria.

- 5.3 Screening:
  - Based on patient feedback, to reduce participant burden because SARS-CoV-2 symptoms may be present, we will offer the opportunity for patients to self-screen online to avoid burden and barriers to participating
    - This will be performed via a web-based form. Eligibility criteria and medical history will be by self-report entries into the secure web-based form.
    - After self-screening online, patients may elect to self-consent online, or have a consent discussion with an RC (section 5.4).
  - For patients who do not want to screen or consent via web-based form, screening and consent may be done over the phone with RC with eligibility criteria and history entered into the web-based form by the RC.
  - Patients will be asked to submit proof of their positive SARS-CoV-2 result via secure means, but the receipt of the result may occur after enrollment.
    - 5.3.1 GFR

GFR will be collected on persons > age 75 years or persons of any age who select or respond that they have chronic kidney disease, heart failure, or liver disease if a GFR is not available within 2 weeks in the EHR. It may be collected from patients by either self-collection kits sent to patients' homes with return arranged by the study team; or by local in-person collection.

Participants will receive the study drug at the same time as the GFR testing kit in the mail (or GFR drawn in person), as well as a return envelope for the study drug. They will start the study drug before their GFR result is returned. If the GFR result returns and is < 45ml/min, they will be asked to stop taking the study drug and return the remainder of the study drug. This will count as a screen failure.

We are taking this approach for 3 reasons: a) this is consistent with clinical practice in which metformin us often started while a GFR result is pending, because the use of metformin for two weeks at a dose of 1,500mg does not significantly increase risk of lactic acidosis in someone who has no known history of severe heart, liver or kidney injury, including in persons with COVID-19; b) to start the study drug early in the course of the disease, as in real life an outpatient post-exposure prophylactic or treatment therapy would be offered at the time of SARS-CoV-2 exposure or positive infection, c) maintain a virtual study design so as to not create unnecessary exposure and use of PPE by having labs drawn in person. Metformin is FDA approved down to a GFR > 30ml/min, though sometimes used down to a GFR of 15.

For any in-person contact, all measures will be taken to mitigate risk of SARS-CoV-2 exposure to the phlebotomy or study team members, and to the participant.

